### 8.2. *Inclusion Criteria*

Subjects who meet all of the following criteria (see **Table 8.2-1**) may be given consideration for inclusion in this clinical investigation, provided no exclusion criterion (see Section 8.3) is met.

**Table 8.2-1: Inclusion Criteria**

Inclusion Criteria	
For Lithotripsy cohort:
 

1. Subject is undergoing treatment for urinary calculi

2. Subject is willing and able to return for all follow-up visits

 
For BPH cohort:
 

1. Subject is <math>\geq 40</math> years of age

2. Subject with a diagnosis of benign prostatic hyperplasia with lower urinary tract symptoms

3. IPSS (International Prostate Symptom) Score <math>\geq 12</math>

4. Qmax (Peak Flow Rate) <math>\leq 15</math> mL/s

5. Subject is willing and able to return for all follow-up visits

---------------------------	---

### 8.3. *Exclusion Criteria*

Subjects who meet any one of the following criteria (**Table 8.3-1**) cannot be included in this study or will be excluded from this clinical study.

**Table 8.3-1: Exclusion Criteria**

Exclusion Criteria	
For Lithotripsy cohort:
 
 
1. Subject has uncontrolled bleeding disorders and coagulopathy
 
2. Subject has untreated urinary tract infection (UTI)
 
3. Subject requires simultaneous HoLEP procedure
 
 
For BPH cohort:
 
 
1. Subject has a diagnosis of bladder cancer
 
2. Subject has a diagnosis of prostate cancer
 
3. Subject with prostate-specific antigen (PSA) > 10 ng/mL suggestive of prostate cancer is not eligible unless patient has concomitant negative prostate biopsy
 
4. Subject has acute prostatitis, a prostate abscess, or neurogenic bladder
 
5. Subject has urethral stricture disorder
 
6. Subject has uncontrolled bleeding disorders and coagulopathy
 
7. Subject has untreated urinary tract infection
 
8. Subject with simultaneous upper urinary calculi lithotripsy and HoLEP procedure (not applicable to bladder calculi)
 

---------------------------	--

## 9. Subject Accountability

### 9.1. *Point of Enrollment*

A subject will be considered enrolled in the study after the subject signs and dates the informed consent form (ICF) and the lithotripsy/HoLEP procedure is attempted. No study specific (non-standard of care) procedure(s) or assessment(s) can take place until the informed consent is signed.

### 9.2. *Withdrawal*

All subjects enrolled in the clinical study (including those withdrawn from the clinical study) shall be accounted for and documented. If a subject withdraws from the clinical investigation, the reason(s) shall be reported. If such withdrawal is due to problems related to device safety or performance, the investigator shall ask for the subject's permission to follow the subject's status/condition outside of the clinical study.

Reasons for withdrawal include but are not limited to physician discretion and subject choice to withdraw consent. While study withdrawal is discouraged, subjects may withdraw from the study at any time, with or without reason, and without prejudice to further treatment. All applicable electronic Case Report Forms (eCRFs) up to the point of subject withdrawal and an End of Study eCRF must be completed. Additional data may no longer be collected after the point at which a subject has been withdrawn from the study or the subject withdraws consent.

Data collected up to the point of subject withdrawal may be used for study analysis, unless local regulations apply.

### **9.2.1. Voluntary Withdrawal**

Subjects may withdraw from the study at any time. At the time of withdrawal, the Investigator shall document the reason for the withdrawal. For subjects who withdraw from the study and decide to revoke their authorization to use and disclose their medical information, the information that has already been collected in the study record may continue to be used; however, no new information will be obtained or added.

### **9.2.2. Involuntary Withdrawal**

Subjects may be involuntarily withdrawn from the study if the Investigator determines it is in the subject's best interest. If the subject is withdrawn at the investigator's discretion, the reason for withdrawal must be documented in the subject's medical records.

### **9.3. *Lost to Follow-Up***

If a subject fails to return to the clinic and/or is unable to be reached for a follow-up visit the site will attempt to contact the subject and reschedule the missed visit and counsel the subject on the importance of maintaining the assigned visit schedule and ascertain if the subject wishes to and/or should continue in the study.

Before the subject may be considered lost to follow-up, the investigator must make the following attempts to contact the subject:

- Three documented telephone attempts
- One certified letter

If the subject can be reached and no longer wishes to participate in the study, the Investigator shall document the reason for the withdrawal and complete the End of Study eCRF.

If the subject is not able to be reached after the required attempts to contact the subject have been made and the subject has missed two consecutive follow-up visits, the subject may be considered lost to follow-up. The Investigator should document in the subject's medical record the attempts to contact the subject and the reason for withdrawal.

### **9.4. *Subject Status and Classification***

A subject will be considered enrolled after a signed informed consent form is obtained and the lithotripsy/HoLEP procedure is attempted. A subject's participation ends when he or she has completed all phases of the study including the last visit as shown in the Data Collection Schedule (see **Table 10.1-1** and **Table 10.1-2**).

### **9.5. *End-of-Study Definition***

The study is considered completed when participants are no longer being examined or the last participant's last study visit has occurred, and study closeout activities are completed.

A subject is considered to have completed the study after the subject has completed all phases of the study including the last visit shown in the Data Collection Schedule (see **Table 10.1-1** and **Table 10.1-2**).

The end of the study is defined as completion of the final Clinical Study Report.

## 10. Study Methods

### 10.1. *Data Collection*

The data collection schedule is shown in **Table 10.1-1** and **Table 10.1-2**. Assessments will be completed based on standard of care practices at the site. For Lithotripsy Cohort, data from all SOC follow-up visits within 60 days of discharge from final Flexiva Pulse holmium laser Lithotripsy procedure will be collected. For BPH Cohort, data from all SOC follow-up visits within 6 months (180 days + 60 days) of discharge from HoLEP procedure will be collected. All study data will be recorded on source documentation and captured within electronic Case Report Forms (eCRFs) for the purposes of this study. Study data will be monitored by Boston Scientific or representatives and as applicable on a regular basis as outlined in the study Monitoring Plan.

**Table 10.1-1: Data Collection Schedule - Lithotripsy Cohort**

Procedure/ Assessment	Screening	Baseline 	Lithotripsy Procedure 	Post Procedure Discharge 	Post final Flexiva Pulse holmium laser Lithotripsy Procedure Follow-up (FU) Visits	Unscheduled Visit
					All SOC FU visits within 2 months (60 days) of discharge	
Eligibility criteria	X					
Informed consent process, including informed consent signature date	X					
Demographics		X				
Medical history		X				
Physical examination, including weight and height		X				
Imaging Study Report		X			X 	
Medications		X		X		
Laboratory Blood Analysis for Lithotripsy Cohort: CBC, coagulation testing (PT, PTT, INR), serum creatinine, uric acid, CRP, BMP		X 				
Laboratory Urinalysis/Culture: Pregnancy Test and UTI		X				
Adverse Events assessment			X	X	X	X
Device Deficiency assessment			X	X		
COVID-19 Assessment		X 	X 	X 	X 	X 

X = required

 = If available = If additional Flexiva Fiber holmium laser lithotripsy procedure is performed, complete additional procedure and discharge CRF = Pregnancy test and urinalysis/culture must be completed within 30 days of procedure, and all other baseline data may be within 60 days = At least one imaging study report required within 60 days of discharge for stone free rate assessment

**Table 10.1-2: Data Collection Schedule - BPH Cohort**

Procedure/ Assessment	Screening	Baseline 	HoLEP Procedure	Post Procedure Discharge	Post HoLEP Procedure Follow-up (FU) Visits	Unscheduled Visit
					All SOC FU visits within 6 months (180 days + 60 days) of discharge	
Eligibility criteria	X					
Informed consent process, including informed consent signature date	X					
Demographics		X				
Medical history		X				
Physical examination, including weight and height		X				
Prostate Volume		X				
Medications		X		X		
Laboratory Blood Analysis for BPH Cohort: CBC, coagulation testing (PT, PTT, INR), PSA		X 				
Laboratory Urinalysis/Culture: UTI		X				
Post Void Residual		X 		X 	X 	
IPSS		X 			X 	
Maximum urinary flow rate (Qmax)		X 			X 	
Adverse Events assessment			X	X	X	X
Device Deficiency assessment			X	X		
COVID-19 Assessment		X 	X 	X 	X 	X 

X = required

 = If available = If subject does not have a catheter = Urinalysis/culture must be completed within 30 days of procedure, and all other baseline data may be within 60 days

## **10.2. Study Candidate Screening**

All interested subjects will undergo screening during which their eligibility for the study will be determined. Sites are expected to follow standard of care testing to diagnose and screen subjects for inclusion in the study.

Subjects who do not meet the inclusion/exclusion criteria are considered screen failures.

If the subject has completed the informed consent process and met all inclusion and none of the exclusion criteria, the subject will progress to the Lithotripsy/HoLEP procedure and follow-up phase of the study.

### **10.2.1. Strategies for Recruitment and Retention**

Subjects will be recruited from clinician practice who are receiving device as standard of care.

## **10.3. Informed Consent**

Written informed consent must be obtained from all potential study candidates before any study specific, non-standard of care screening tests or procedures are performed. Only current Institutional Review Board (IRB), Ethics Committee (EC) or Research Ethics Board (REB) approved study specific ICF must be used. Study personnel should explain that even if a subject agrees to participate in the study and signs an ICF, certain screening procedures might demonstrate that the subject is not eligible to continue participation. Written informed consent must be recorded appropriately by means of the subject's dated signature.

## **10.4. Screening Assessments/Procedures**

The Screening and Baseline visits may occur on the same day or on different days. The following must be completed prior to collecting baseline data described in section 10.5:

- Review of Eligibility Criteria
- Informed Consent Process, including informed consent signature

## **10.5. Baseline Visit**

The Baseline Visit and assessments will occur prior to the subject having Lithotripsy/HoLEP procedure. Pregnancy test and urinalysis/culture must be completed within 30 days of procedure, and all other baseline data may be completed within 60 days of procedure.

The baseline assessments below can be completed on the same day as Screening.

### Baseline Assessments for both cohorts

- Demographics: Age, Gender, Race and Ethnicity

- Medical History: Only current medical conditions in the past 12 months prior to Baseline assessment and lifetime history of stones and/or BPH (including all surgical and medical treatments).
- Physical Examination
- Medications: only active medications at Baseline and lifetime history of medications for treatment of stones and/or BPH.
- Urinalysis/culture
- Urinary Tract Infection status
- COVID-19 assessment: prior diagnosis, test result, vaccination status (if available)

#### Baseline Assessments for Lithotripsy cohort only

- Imaging Study Report: Computed Tomography (CT) or x-ray or ultrasound of kidneys, ureters, and bladder (KUB) – Lithotripsy cohort only
- Laboratory Blood Tests (if available): Complete Blood Count (CBC), coagulation testing (Prothrombin Time, Partial Thromboplastin Time, International Normalized Ratio), serum creatinine, uric acid, C-Reactive Protein, Basic Metabolic Panel
- Pregnancy test for women of child-bearing potential

#### Baseline Assessments for BPH cohort only

- Prostate Volume – BPH cohort only
- Laboratory Blood Tests (if available): Complete Blood Count, coagulation testing (Prothrombin Time, Partial Thromboplastin Time, International Normalized Ratio), Prostate Specific Antigen
- International Prostate Symptom Score (IPSS) – except if patient is catheterized and IPSS cannot be done.
- Maximum urinary flow rate (Qmax) – except if patient is catheterized and uroflow test cannot be done (if available)
- Post Void Residual (PVR), except if patient is catheterized and PVR cannot be done (if available)

#### **10.6. *Lithotripsy/HoLEP Procedure Visit***

Lithotripsy/HoLEP procedure is defined as the start time of sedation and/or anesthesia and includes the entirety of the holmium laser Lithotripsy or HoLEP procedure. The procedure will be performed by a trained physician and per the Flexiva Pulse Laser Fiber IFU.

It is recommended that surgeons perform a second evaluation at the time of the lithotripsy procedure to ensure all stones have been removed.

If multi-staged lithotripsy procedures are performed using the Flexiva Pulse Laser Fibers, then data will also be collected on the additional procedures. **If the additional lithotripsy procedure performed does not use the Flexiva Pulse Laser Fibers, then subject should be exited from the study at the time of the additional procedure.**

If subject is undergoing HoLEP and simultaneous holmium laser lithotripsy using Flexiva Pulse Laser Fibers to remove bladder calculi, data will also be collected on the lithotripsy procedure.

Baseline visit information may be collected on same day, prior to the Lithotripsy/HoLEP procedure.

After the Lithotripsy/HoLEP procedure, the following data will be collected:

- Procedure information and evaluation of applicable BSC devices used. It is recommended that User Feedback Evaluations are **completed within 1 week of procedure.**
- Fiber Information – type, size, number of fibers used, model of scope, number of passes per fiber, fiber fracture, fiber deflection, if fiber was stripped/cleaved
- Fiber Performance – fiber tip degradation
- Assessment of adverse events and device deficiencies
- COVID-19 assessment: prior diagnosis, test result, vaccination status (if available)

#### **10.7. Post-Procedure Discharge**

At the time of post-procedure discharge, the following information will be collected:

##### Lithotripsy Cohort

- Medications
- Assessment of adverse events and device deficiencies
- COVID-19 assessment: prior diagnosis, test result, vaccination status (if available)

Note: If multi-staged procedures are performed using the Flexiva Pulse fibers, then discharge data will also be collected on the additional procedures.

##### BPH Cohort

- Medications
- Post Void Residual (PVR) if subject is discharged to home without a catheter (if available)
- Assessment of adverse events and device deficiencies
- COVID-19 assessment: prior diagnosis, test result, vaccination status (if available)

### **10.8. Post Lithotripsy/HoLEP Procedure Follow-up Visits**

#### **10.8.1. All SOC Follow-up Visits within 60 days post discharge from final Flexiva Pulse holmium laser Lithotripsy procedure**

For any follow-up visit(s) that occurs within 60 days post discharge from final Flexiva Pulse holmium laser lithotripsy procedure per site's standard of care, the following assessments will be performed and data points collected if available:

- Imaging Study Report: Computed Tomography (CT) or x-ray or ultrasound of kidneys, ureters, and bladder (KUB). **At least one imaging study report is required within 60 days of discharge for stone free rate assessment.**
- Assessment of adverse events
- COVID-19 assessment: prior diagnosis, test result, vaccination status
- Study Exit at last follow-up visit within 60 days post discharge

#### **10.8.2. All SOC Follow-up Visits within 6 months (180 days + 60 days) post discharge from HoLEP procedure**

For any follow-up visit(s) that occur within 6 months (180 days + 60 days) post discharge from HoLEP procedure per site's standard of care, the following assessments will be performed and data points collected:

- Post Void Residual (if available)
- International Prostate Symptom Score (IPSS)
- Maximum urinary flow rate (if available)
- Assessment of adverse events
- COVID-19 assessment: prior diagnosis, test result, vaccination status (if available)
- Study Exit at last follow-up visit within 6 months (180 days + 60 days) post discharge

### **10.9. Unscheduled Visit**

Subjects may have additional visits (other than the study visits specified above), that are unplanned visits and are considered as unscheduled visits. Some examples of these visits may include a visit for a change in symptoms or to check on a medical event that could not be resolved during one of the scheduled study visits.

If an unscheduled visit occurs, the following information will be collected:

- Assessment of adverse events
- COVID-19 assessment: prior diagnosis, test result, vaccination status (if available)

### **10.10. *Study Completion***

Each subject in the Lithotripsy cohort will be followed up to 60 days post discharge from final Flexiva Pulse holmium laser Lithotripsy procedure per site's SOC. Each subject in the BPH cohort will be followed up to 6 months (180 days + 60 days) post discharge from HoLEP procedure per site's SOC. All subjects completing the last follow-up visit per site's SOC and their respective cohorts, will be considered to have completed the study. Subjects with any ongoing Adverse Events at the end of the study should be followed per institutions' standard of care.

If subject in the Lithotripsy cohort is undergoing a multi-staged lithotripsy procedure that does not use the Flexiva Pulse Laser Fibers, then subject should be exited from the study at the time of the additional procedure.

### **10.11. *Source Documents***

It is preferable that original source documents are maintained, when available. In lieu of original source documents, certified copies are required to be maintained. A certified copy is a copy (irrespective of the type of media used) of the original record that has been verified (i.e., by a dated signature or by generation through a validated process) to have the same information, including data that describe the context, content, and structure, as the original.

### **10.12. *Local Laboratory documentation***

The laboratory (blood and urine) analysis, collected in the study will be completed at the local centers per standard of care. Appropriate laboratory certifications and documentation records are required to be maintained at the site.

## **11. Statistical Considerations**

### **11.1. *Endpoints***

#### **11.1.1. Primary Safety Endpoint**

The primary safety endpoint is the occurrence of any Serious Adverse Device Effects (SADE) (including burn, perforation, and hemorrhage) during Lithotripsy and BPH procedures.

##### **11.1.1.1. Hypotheses**

There is no formal hypothesis test. The study is designed to evaluate primary safety endpoints with desired precision.

##### **11.1.1.2. Sample Size**

The sample size justification is based on a confidence interval (CI) approach. As there is limited published literature on the device safety measurement in a clinical study setting, a conservative assumption of 3% SADE rate within 1 month of the procedure for lithotripsy cohort and 5% for BPH cohort within 3 months of the HoLEP procedure was assumed. Ninety

(90) subjects are needed for each cohort to construct a 95% two-sided CI with a maximum width of 8.4% for lithotripsy cohort and 10.2% for HoLEP cohort. Assuming 10% attrition within 1 month of the procedure for lithotripsy cohort and within 3 months of the HoLEP procedure, it is anticipated that 100 treated subjects will be required for each procedure cohort.

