#### **11.1.1.3. Statistical Methods**

A two-sided 95% confidence interval will be constructed using exact (Clopper-Pearson) method to estimate the SADE rate at 30 days post procedure for lithotripsy cohort and the SADE rate at 3-month post procedure for BPH cohort.

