### ***11.2. General Statistical Methods***

#### **11.2.1. Analysis Sets**

The Intent-to-Treat (ITT) subject population includes all subjects who provide written informed consent to be enrolled into the study, and have the Lithotripsy or BPH procedure attempted.

The As Treated (AT) subject population includes all the ITT subjects who had the Lithotripsy or BPH procedure completed.

The Per Protocol (PP) subject population includes all the AT subjects who also meet all eligibility criteria and have no major protocol deviations.

The primary analysis of all the endpoints will be performed for the ITT population. Efficacy endpoints will be evaluated for the PP population as a sensitivity analysis and safety endpoints will be evaluated for the AS population as a sensitivity analysis.

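### The confidence-interval widths of 8.4% and 10.2% at n = 90 are widths at the assumed SADE rates, not maxima

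*Combined protocol and SAP*

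**What the plan says.** The study has no hypothesis test. Section 11.1.1.1 rests the design on precision: "The study is designed to evaluate primary safety endpoints with desired precision".

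Section 11.1.1.2 sets the inputs, calling them "a conservative assumption of 3% SADE rate within 1 month of the procedure for lithotripsy cohort and 5% for BPH cohort" (the latter within 3 months of HoLEP). It then states that 90 "subjects are needed for each cohort to construct a 95% two-sided CI with a maximum width of 8.4% for lithotripsy cohort and 10.2" percent for the HoLEP cohort, and adds 10% attrition to reach 100 treated subjects per cohort. The Synopsis (Section 2, Sample Size Parameters) repeats the statement.

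Section 11.1.1.3 fixes the interval method: "A two-sided 95% confidence interval will be constructed using exact (Clopper-Pearson) method". Section 11.2.1 fixes the population: "The primary analysis of all the endpoints will be performed for the ITT population". Section 11.3 restricts analyses to available cases unless otherwise specified.

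Neither the Synopsis nor Section 11 says that the widths hold only at or below particular observed rates, and no widths are given for other event counts.

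**The concern.** The width of an exact binomial interval depends on the observed count. For a rare event it grows with every additional event. A maximum width at n = 90 therefore needs either a cap on the number of events or a probability attached to it, and the plan gives neither.

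Since no hypothesis is tested and no power is computed, the width statement is the whole quantitative case for 90 evaluable and 100 treated subjects per cohort. A reader who takes it at face value would believe that the SADE interval cannot be wider than 8.4 or 10.2 points, and might report that as a guaranteed property of the design.

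**Working it through.** **Inputs.** n = 90 per cohort; assumed SADE rates of 3% (lithotripsy) and 5% (BPH); two-sided 95% level; stated widths of 8.4 and 10.2 points (all Section 11.1.1.2). Clopper-Pearson method (Section 11.1.1.3).

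**Formula.** For x events in n subjects:
- lower limit = BetaInv(0.025; x, n − x + 1)
- upper limit = BetaInv(0.975; x + 1, n − x)
- width = upper − lower

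**Step 1: reproduce the plan's figures.** Use the expected counts.
- Lithotripsy: x = 0.03 × 90 = 2.7. Limits 0.552% to 8.953%, width 8.40 points.
- BPH: x = 0.05 × 90 = 4.5. Limits 1.519% to 11.746%, width 10.23 points.

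These round to 8.4 and 10.2. Other interval methods do not give both figures: Wald 6.52 and 9.01; Wald with continuity correction 8.16 and 10.12; Wilson 7.90 and 9.56; Agresti-Coull 8.76 and 10.22; Jeffreys 7.34 and 9.16. The attrition step also reproduces: 90 / 0.9 = 100.

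The arithmetic is sound, but 2.7 and 4.5 events cannot be observed.

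**Step 2: widths at counts that can occur, n = 90.**

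| Events | Observed rate | Width (points) | Within 8.4? | Within 10.2? |
|---|---|---|---|---|
| 0 | 0.00% | 4.02 | yes | yes |
| 1 | 1.11% | 6.01 | yes | yes |
| 2 | 2.22% | 7.53 | yes | yes |
| 3 | 3.33% | 8.74 | no | yes |
| 4 | 4.44% | 9.77 | no | yes |
| 5 | 5.56% | 10.66 | no | no |
| 6 | 6.67% | 11.46 | no | no |
| 7 | 7.78% | 12.19 | no | no |

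The lithotripsy figure is a bound for 0–2 events and the BPH figure for 0–4. The first overshoots are 8.74 − 8.4 = 0.34 and 10.66 − 10.2 = 0.46 points. The unconditional maximum at n = 90 is 21.46 points, at 45 events, which has no practical relevance for a rare SADE. By symmetry the bounds also hold at 88–90 and 86–90 events, which is equally irrelevant.

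**Step 3: how often the stated figure is exceeded, X ~ Binomial(90, p).**
- Lithotripsy, p = 3%: P(X ≥ 3) = 1 − (0.0645 + 0.1795 + 0.2470) = 0.509.
- BPH, p = 5%: P(X ≥ 5) = 1 − (0.0099 + 0.0468 + 0.1097 + 0.1694 + 0.1939) = 0.470.

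At lower true rates:
- Lithotripsy: 0.269 at 2%, 0.062 at 1%.
- BPH: 0.292 at 4%, 0.134 at 3%.

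**Step 4: mean width at the assumed rates.** Weighting each width by its binomial probability at n = 90 gives 8.12 points (3%) and 9.98 points (5%). The stated figures lie close to an average width.

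**Step 5: if all 100 treated subjects are evaluable.** Widths are 7.89 at 3/100 and 8.83 at 4/100 (lithotripsy), and 9.64 at 5/100 and 10.37 at 6/100 (BPH). The stated figures then bound the width for 0–3 and 0–5 events. At the assumed rates they are exceeded with probability P(X ≥ 4) = 0.353 and P(X ≥ 6) = 0.384.

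**The case against.** The strongest defence is a conditional reading. The sentence just before the widths calls the 3% and 5% rates conservative, so *maximum* can be taken to mean the width if the rate is no higher than assumed. At n = 90, an observed rate of at most 3% means 0–2 events and at most 5% means 0–4 events, exactly the counts at which the stated figures do bound the width.

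That reading is coherent, but the condition is not written down. It must also refer to the observed rate. A true rate at or below the assumption does not secure the bound, since exceedance is still 0.27 at a true 2% (lithotripsy) and 0.29 at a true 4% (BPH).

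Three further points are fair:
- The sponsor's calculation is correct; the fault lies in one word.
- The probabilities 0.51 and 0.47 are the unfavourable case. They need the true rate to equal a value the plan calls conservative and exactly 90 evaluable subjects. They drop at lower rates and with 100 evaluable, although they do not vanish.
- Nothing in the study turns on the width. There is no hypothesis test, no formal interim analysis for effectiveness or futility is planned (Section 11.3.3), and the reported interval will be exact whatever the count.

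These points limit the weight of the concern. They do not make the statement true as written.

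**Conclusion.** The concern holds and is minor. The stated widths are correct Clopper-Pearson widths at the assumed rates, but they are wrong as maxima. At n = 90 they are exceeded from 3 SADEs in the lithotripsy cohort and from 5 in the BPH cohort. If the true rates equal the assumed 3% and 5%, that is close to an even chance in each cohort (0.51 and 0.47).

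The result rests on the plan's own method and inputs, on independent subjects with a common SADE probability within each cohort, and on 90 evaluable subjects. With 100 evaluable the conclusion is the same and the probabilities are 0.35 and 0.38. Neither the sample size nor the planned analysis is affected.

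**What to change.** In the Synopsis (Sample Size Parameters) and Section 11.1.1.2, delete *maximum* and replace the width statement with wording such as:

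> At the assumed SADE rates, 90 evaluable subjects per cohort give an exact 95% CI width of approximately 8.4 percentage points (lithotripsy) and 10.2 percentage points (BPH). The width is 7.5 or 8.7 points for 2 or 3 observed SADEs (lithotripsy), and 9.8 or 10.7 points for 4 or 5 (BPH).

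The first sentence alone removes the error; the second shows the reader how the width moves with the count. The cost is two sentences in two places and a slightly less favourable precision statement.
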